The protocol, informed consent form(s), and all participant materials will be submitted to the Institutional Review Board (IRB) for review and approval. Approval of both the protocol and the consent form must be obtained before any participant is enrolled. Any amendment to the protocol will require review and approval by the IRB before the changes are implemented to the study. In addition, all changes to the consent form will be IRB-approved; a determination will be made regarding whether a new consent needs to be obtained from participants who provided consent, using a previously approved consent form.

1 PROTOCOL SUMMARY

[figure not shown]
1.1 SYNOPSIS

[figure not shown]
[figure not shown]
- Title:** Advanced R²Eperfusion STRategies for Refractory Cardiac Arrest (ARREST Trial)
- Study Description:** This is a Phase II, single center (Under the Center for Resuscitation Medicine at the University of Minnesota Medical School), partially blinded, prospective, intention to treat, safety and efficacy clinical trial, randomizing adult patients (18-75 years old) with refractory ventricular fibrillation/pulseless ventricular tachycardia (VF/VT) out-of-hospital cardiac arrest (OHCA) who are transferred by emergency medical services (EMS) with ongoing mechanical cardiopulmonary resuscitation (CPR) or who are resuscitated to receive one of the 2 local standards of care practiced in our community:
- 1) Early Extracorporeal Membrane Oxygenation (ECMO) Facilitated Resuscitation:** Regardless of whether return of spontaneous circulation (ROSC) has been achieved and with on-going mechanical CPR, patients will enter the Cardiac Catheterization Laboratory (CCL) for expeditious VAECMO initiation, if required, followed by coronary angiography and percutaneous coronary intervention (PCI) when appropriate.
- 2) Standard Advanced Cardiac Life Support (ACLS) Resuscitation:** Patients with refractory VF/VT OHCA will be treated with ACLS resuscitation for at least 15 minutes after arrival in the emergency department (ED), or up to 60 minutes from 911 call, after which the physician (MD) can continue resuscitation efforts until ROSC is achieved or futility has been reached based on their clinical judgment. If the patient has not achieved ROSC during the times mentioned above, the ED MD can declare death when he or she believes that ACLS is futile. If ROSC is present upon arrival or has been achieved anytime during resuscitation in the ED, the patient will be taken to the cardiac catheterization laboratory (CCL) for coronary angiography and PCI, and potential VA ECMO or other circulatory support device initiation, as clinically indicated.
- Objectives:** The **Early ECMO Facilitated Resuscitation** Arm of the study, will expedite circulatory support, mitigate metabolic derangement, facilitate the identification and treatment of reversible coronary artery disease (CAD) and significantly improve functionally favorable survival compared with the **Standard ACLS Resuscitation** Arm.
- Endpoints:** **Primary study endpoint.** Survival to hospital discharge.
- Secondary endpoints:** Safety and ECMO-related complications, survival to hospital discharge with modified Rankin Scale Score (mRS) ≤ 3 along with functional status (Cerebral Performance Category [CPC]), 3- and 6-month survival and functional status (mRS score and CPC classification), cost per patient and cost per life saved.
- Population:** The ARREST trial population must have all the inclusion criteria below:

- 1) OHCA of presumed cardiac etiology
- 2) Shockable (VF or VT) as the first presenting rhythm
- 3) Presumed or known to be 18-75 years of age
- 4) Received 3 DC shocks without ROSC.
- 5) Body morphology able to accommodate a Lund University Cardiopulmonary Assist System (LUCAS™) automated CPR device.
- 6) Estimated transfer time from the scene to the ED or CCL < 30 minutes

1.2 SCHEMA

THE ARREST TRIAL - STUDY ALGORITHM FLOW CHART

VA-ECMO or other circulatory support device initiation. Suggested common clinical indications once in the CCL with ROSC:

- Profound cardiogenic shock with SBP< 90 mmHg or MAP <60mmHg despite inotropic support and an intra-aortic balloon pump,
- Persistent hypoxia with arterial oxygen saturation <90% despite maximum ventilatory support,
- Florid pulmonary edema despite iv diuretics,
- Recurrent episodes of VF or VT in the CCL.

Outcomes are reported in the ITT primary endpoint.

1.3 SCHEDULE OF ACTIVITIES (SOA)

The ARREST Trial is a pragmatic clinical trial randomizing study subjects to one of two standards of care practiced in the community. Treatment of patients in both groups is solely at the discretion of the treating clinician.

Assessment	Hospitalization	Discharge from Hospital	3 month visit ¹ (±14 Days)	6 month visit ¹ (±30 Days)
Inclusion/Exclusion	X			
Randomization	X			
Continued Participation Informed Consent	X			
Demographics	X			
Medical History	X			
Pre-hospital data	X			
Hospital data	X			
Data collection on procedures done during hospitalization	X			
Data collection labs done during hospitalization	X			
Blinded mRS score		X	X	X
Blinded CPC Score		X	X	X
AE/SAE reporting	X	X	X	X
UB04		X		

¹ Calculated from day of Discharge

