3 OBJECTIVES AND ENDPOINTS

Primary Objective.

The Minneapolis/St. Paul community has established 2 standards of care for adult patients with refractory VF/VT OHCA, incorporating early emergency medical services (EMS) transport of patients to a higher level of care, both of which may include implementation of ECMO if available. The overall objective of this study is to assess the rate of survival to hospital discharge in adult patients (18-75 years) with refractory VF/VT OHCA treated with one of these two local standards of care: 1) **Early ECMO Facilitated Resuscitation**: early ECMO access for circulatory support and PCI, when needed, or 2) **Standard ACLS Resuscitation**: continued ED-based ACLS resuscitation until achievement of ROSC or Death declaration.

In both arms, patients with ROSC will be taken to the cardiac catheterization laboratory (CCL) for angiography and percutaneous coronary intervention (PCI), as clinically indicated. VA ECMO can be initiated in some of those patients for clinical indications for cardiorespiratory failure based on the judgment of the interventional cardiologist and will be reported on an intention-to-treat manner. As an important secondary endpoint, functional status (Modified Rankin Scale score of 3 or less [mRS \leq 3] and CPC \leq 2) will be determined at hospital discharge, 3, and 6 months in both patient groups.

Primary Efficacy Endpoint:

- Survival to hospital discharge

Justification: Survival is the most widely accepted endpoint in CPR and OHCA trials. Our trial is designed to evaluate the effect of expediting normalization of circulation with artificial means (ECMO initiation) in order to facilitate survival.

Secondary Objective.

Longer Term Outcome: We will assess the rates of survival to hospital discharge with mRS \leq 3, 3- and 6-month survival, survival to 3 and 6 months with mRS \leq 3, and functional status at discharge, 3 and 6 months (mRS and Cerebral Performance Category [CPC] scores).

Safety: We will assess the frequency of serious adverse events (SAEs) and frequency of ECMO-related complications in the two groups.

Cost: The cost per patient and cost per life saved in the two groups will be determined based on billing charges assessed by the UB-04 form.

Secondary Efficacy Endpoints:

- Survival to hospital discharge with mRS \leq 3
- Survival to 3 and 6 months,
- Survival to 3 and 6 months with mRS \leq 3,

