4.3 SCIENTIFIC RATIONALE FOR STUDY DESIGN

Primary Hypothesis. Based on the promising preliminary experience, we hypothesize that the **Early ECMO Resuscitation Arm**, with early ECMO access for circulatory support and PCI, when needed, will facilitate cardiorespiratory stabilization as well as identification and treatment of reversible CAD and significantly improve survival to hospital discharge compared with the **Standard ACLS Resuscitation Arm**. Many patients that survive from the OHCA and are discharged continue to improve over 3-6 months. As such, we will assess their functional status at hospital discharge, 3 and 6 months to fully capture the potential for improvement in this population.

Early identification of reversible causes of refractory VF arrest and circulatory support appears to provide a benefit, but without randomization it is impossible to determine if the patients that survive would have survived in the absence of early ECMO initiation or they could have achieved ROSC without early ECMO initiation.

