6 STUDY INTERVENTION

6.1 STUDY INTERVENTION(S) ADMINISTRATION

6.1.1 STUDY INTERVENTION DESCRIPTION

The ARREST study is a pragmatic clinical trial. Other than randomization to one of two arms [**Early ECMO Facilitated Resuscitation Arm** versus **Standard ACLS Resuscitation Arm**] there are no specified study interventions. All surviving patients will have their mRS and CPC score at hospital discharge determined; survival, mRS score, and CPC classification determined at 3 months post hospital discharge; and survival, mRS, and CPC classification determined at 6 months post hospital discharge. Cost per patient, cost per life saved (based on billing charges), safety and ECMO-related complications for the two treatment groups will also be determined.

Screening and Randomization.

There is no recruitment for this study as it is not possible to prospectively identify victims of out-of-hospital cardiac arrest. The subjects will be enrolled under exception from informed consent, 21 CFR 50.24.

EMS providers will deliver standard resuscitation procedures according to their standard practice. If the patient does not have ROSC following 3 defibrillations, EMS providers will call a central dispatch number per standard clinical practice, providing the research team with notification of a potentially eligible ARREST Trial study subject. At the same time the CCL/ECMO team is notified and activated. Immediately following hospital arrival, the research team will evaluate the ARREST Trial inclusion and exclusion criteria and, if eligible, randomize and enter the patient in the study, transferring the patient to the ED or CCL according to group allocation.

No Study Treatment; The following are suggested clinical practices that may or may not occur based on the judgment of the treating physician.

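### The 3- and 6-month survival, mRS and CPC endpoints are timed from hospital discharge, so time since randomisation at assessment varies with length of stay and may differ between arms

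*Combined protocol and SAP*

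**What the plan says.** The footnote to the schedule in section 1.3 applies to both follow-up visits and reads "Calculated from day of Discharge". The windows are ±14 days at 3 months and ±30 days at 6 months. Section 6.1.1 agrees for the first of these visits: "survival, mRS score, and CPC classification determined at 3 months post hospital discharge". It words the second visit, at 6 months, in the same way. Section 9.4.1 repeats both in the statistical plan.

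The endpoint lists in sections 3, 9.1 and 9.4.3 give no time origin; section 3, for example, has only "survival to 3 and 6 months with mRS \leq 3". Nowhere are these outcomes counted from randomisation or from the arrest. Section 6.3 places randomisation immediately after hospital arrival.

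The reason given for late assessment, in section 4.3 and similarly in section 3, is that "Many patients that survive from the OHCA and are discharged continue to improve over 3-6 months".

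**The concern.** Because randomisation is at the hospital door, the whole hospital stay is a post-randomisation quantity that treatment can affect. With a discharge anchor, 3 months is not a fixed landmark: a patient who stays 10 days is assessed around day 100 and one who stays 40 days around day 130. If mean stay among survivors differs between arms, one arm is assessed later after the arrest than the other.

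Two things are then at stake for the secondary endpoints. Survival proportions would not refer to the same time since randomisation in both arms. The mRS and CPC comparison could partly reflect unequal recovery time, since the protocol's own rationale is that function is still changing over this period.

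**Working it through.** **Inputs from the documents.** Anchor: day of discharge (1.3, 6.1.1, 9.4.1). Windows: ±14 and ±30 days (1.3). Randomisation: on hospital arrival (6.3). Expected ECMO support: 3 to 5 days or longer in patients of either group who receive it, with 3.0 ± 2.0 days in the earlier cohort (6.1.1, ECMO Exposure). Design survival rates: 37% and 12% (9.1, 9.2). Length of stay, overall or by arm: not given.

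**The plan's own figures.** There is none for this point. The only operating characteristics concern survival to discharge. Re-simulating that design (10,000 trials per scenario, first 30 patients split 15:15 by assumption) gives power 0.904 against the stated 0.905 and type I error 0.047 against 0.048. These do not involve the follow-up clock and do not change.

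**Step 1: assessment time.** With L the length of stay in days, time from randomisation is L + 90 at the 3-month visit and L + 180 at the 6-month visit. The between-arm shift is the difference d in survivors' mean stay at both visits. With a randomisation anchor the planned shift is 0.

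| Assumed d (days) | Share of 90 days | Share of 180 days | Beyond ±14 days? | Beyond ±30 days? |
|---|---|---|---|---|
| 5 | 6% | 3% | no | no |
| 10 | 11% | 6% | no | no |
| 20 | 22% | 11% | yes | no |
| 30 | 33% | 17% | yes | no (equal) |

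The d values are illustrations. If ECMO added only its own run time of 3 to 5 days, in one arm only, the shift would be 3/90 = 3% to 5/90 = 6% of the 3-month interval, well inside the visit window.

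**Step 2: binary survival.** Assume mortality m of 2% to 10% in the 6 months after discharge at a constant hazard h = −ln(1 − m)/180, a 20-day stay in the standard arm, and 20 + d days in the ECMO arm.

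- Discharge clock: difference = (0.37 − 0.12) × exp(−90h).
- Randomisation clock, day 90: difference = 0.37 × exp(−h(70 − d)) − 0.12 × exp(−70h).

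For m = 2%, d = 5: 0.2475 against 0.2482, a change of about 0.1 percentage points. For m = 10%, d = 30: 0.2372 against 0.2463, a change of 0.9 points. Part of the latter arises even with equal stays: at m = 10%, d = 0, the randomisation clock gives 0.25 × exp(−70h) = 0.2400, already 0.3 points above 0.2372. The unequal stay therefore contributes about 0.6 points at the extreme.

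In-hospital deaths, 63% and 88% of patients at the design rates (1 − 0.37 and 1 − 0.12), are failures on both clocks. Only deaths between the two landmarks can change classification.

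**Step 3: mRS and CPC.** The documents give no rate of functional change per week, so no effect can be computed. All that follows is that assessment time can matter if function is still improving.

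**The case against.** The strongest defence is that the anchor is a consistent, pre-specified choice that suits a question about recovery after discharge. Section 2.2 frames the expected functional benefit as emerging by 3 to 6 months after discharge, and section 2.1 says function improves following discharge. That supports assessing late. It does not require discharge as the origin: 90 and 180 days from randomisation are also late assessments.

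A reader might go further than the documents allow in three ways.

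- **That stays are likely to be longer in the ECMO arm.** ECMO is routine in one arm and conditional on ROSC in the other, so this is tempting. But the follow-up clock concerns survivors only. Standard-arm survivors have regained ROSC, go to the catheterisation laboratory and may receive ECMO there (4.1, 6.1.1). The 3-to-5-day expectation covers ECMO recipients in both groups, and all survivors follow the same intensive care protocol (4.1, 6.3). A difference is possible; its direction is not established.
- **That the functional comparison is tilted.** Later assessment gives more recovery time but also more time at risk of death. For survival with mRS of 3 or less the net direction is therefore unknown. Section 2.1 also reports that the 26 favourable survivors in the centre's first cohort had CPC 1 at 3 months, which gives little sign that a week or two would move CPC. It says nothing about mRS.
- **That in-hospital deaths have no clock start and so leave the endpoint undefined.** These are binary outcomes analysed by Fisher's exact test or a logistic model (9.4.3). A patient who dies in hospital has not survived to 3 or 6 months on any clock. What remains is only that the definition should say so.

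It is also fair that mRS and CPC at discharge depend on length of stay, and that re-anchoring the later visits leaves this unchanged.

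**Conclusion.** The point holds as a modest one about secondary endpoints. The discharge anchor is explicit in three sections, and it makes time since randomisation at assessment equal to length of stay plus 90 or 180 days. Whether that time differs between arms, by how much and in which direction cannot be determined from the documents.

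The effect on 3-month survival is probably under 1 percentage point, given post-discharge mortality of 2% to 10%, a constant hazard, a 20-day standard-arm stay and a stay difference of 5 to 30 days, all of which are assumptions. mRS and CPC could be affected to an unknown degree. The primary endpoint, the 0.986 threshold, the sample size and the allocation rule are untouched. It is worth correcting because the correction is cheap, not because the trial's conclusions are shown to be at risk.

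**What to change.** In sections 1.3, 6.1.1 and 9.4.1, define 3- and 6-month survival, mRS and CPC at 90 and 180 days from randomisation, keeping the ±14- and ±30-day windows. State that in-hospital deaths count as non-survivors. Report by arm the length of stay and the days from randomisation to each mRS assessment; the latter also makes the timing of the discharge assessment visible.

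If the discharge-based visits are kept, at least analyse survival at 90 and 180 days from randomisation, which needs only vital status and dates of death.

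The cost is small. Wording changes and follow-up contacts are rescheduled, which is easy because section 6.3 already allows telephone assessment. A rare patient still in hospital at day 90 is assessed there. The endpoint would no longer describe a fixed period after discharge, which is the one thing the present anchor provides.

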2 INTRODUCTION

2.1 STUDY RATIONALE

More than 350,000 people in the United States die from out-of-hospital cardiac arrest (OHCA) each year.^{1,2} Although survival rates are higher in OHCA patients with a shockable rhythm, i.e., ventricular fibrillation/pulseless ventricular tachycardia (VF/VT; 21-35%) compared with those with a nonshockable rhythm (1-8%),²⁻⁹ more than 50% of patients with VF/VT OHCA are refractory to current treatment and never achieve return of spontaneous circulation (ROSC), or die before they are admitted to the hospital.² Acute or chronic coronary artery disease (CAD) is present in 70-84% of patients with **refractory** VF/VT cardiac arrest,^{4, 10-19} and we believe that it is the burden of significant CAD that limits the ability of conventional CPR to successfully resuscitate these patients. Coronary stenosis or occlusion can now be potentially reversed by advanced perfusion/reperfusion strategies.^{11, 12, 19} Thus, although patients with refractory VF/VT represent the subgroup with the worst prognosis (85-90% mortality), the underlying cause of cardiac arrest is likely to be reversible in most of these patients. It is this subgroup that offers the greatest opportunity to impact survival and public health.

The treatment strategy for patients with refractory VF/VT cardiac arrest should clearly include achievement of adequate coronary and cerebral perfusion by using mechanical CPR devices, optimizing CPR hemodynamics, facilitating early transport, and providing ongoing treatment during transport. Compared with a strategy that provides these measures but requires ROSC before the patient can gain access to the cardiac catheterization laboratory (CCL), the addition of circulatory support using extracorporeal membrane oxygenation (ECMO), which can function as the stabilization platform to facilitate percutaneous coronary intervention (PCI) when clinically indicated, is expected to significantly improve functionally favorable survival to hospital discharge. To implement these strategies, we instituted the Refractory VF/VT clinical pathway as a standard of care in Minneapolis/St. Paul (MSP), Minnesota, through a community-wide, comprehensively integrated, collaboration called the Minnesota Resuscitation Consortium (MRC).^{11, 12} During the first 12 months, 62 sequential OHCA patients entered the CCL with CPR in progress. Significant CAD was present in 84% (52/62), with an average syntax score of 29 ± 14 .¹¹ Overall, 45% (28/62) survived to hospital discharge, and 42% (26/62) survived to hospital discharge with good neurological function (Cerebral Performance Category [CPC] 1 or 2) and had a CPC score of 1 at 3 months.¹¹ The results have stayed consistent over the 30 months of operations with survival being maintained around 40-45%. Historical data for patients in the same population who received Amiodarone and standard resuscitation practice showed a survival rate of 15%, with CPC 1 or 2.¹¹ In our 2.5 year experience, we have treated 152 patients with average CPR duration of 61 ± 2.1 minutes and survival with CPC 1 or 2 has remained at 40%. Our experience with this clinical protocol suggests that survival rates may be higher with routine, **early ECMO facilitated resuscitation** compared to the conventional resuscitation practice in which either ROSC is required for CCL access. Our experience to date also indicates functionally favorable survival improves following hospital discharge and continues improving up to 3-6 months. However, because widespread use of emergent ECMO initiation at short notice with field activation would require major infrastructural investments, both the

contribution and relative cost of routine, **early ECMO facilitated resuscitation** to the management and survival of this population need to be assessed in a randomized trial.

ARREST Trial hypothesis. Based on our preliminary results, we hypothesize that routine **early ECMO facilitated resuscitation** will expedite circulatory support, mitigate metabolic derangement, facilitate the identification and treatment of reversible CAD and significantly improve survival to hospital discharge compared with ED-based **standard ACLS resuscitation**.

ARREST Trial. We propose a Phase II, single center, partially blinded, intention to treat, safety and efficacy clinical trial to assess the results of routine **early ECMO facilitated resuscitation** compared with ED-based **standard ACLS resuscitation**. Both strategies represent current standards of care **in our community**. The Minnesota Resuscitation Consortium (MRC) has the patient population, experience, expertise, and infrastructure to successfully execute the proposed study. Two EMS systems currently transport patients to an ED for the **standard ACLS resuscitation**, and three EMS systems transport patients to the University of Minnesota for the routine **early ECMO facilitated resuscitation**.

Specific Aim. The primary objective is to assess the rates of survival to hospital discharge in adult patients (aged 18-75 years) with refractory VF/VT OHCA who are transported to the University of Minnesota and randomized to treatment under the **early ECMO facilitated resuscitation** arm compared with those treated under the **standard ACLS resuscitation**.

Primary Study Endpoint Survival to hospital discharge.

Secondary Endpoints Secondary efficacy endpoints include survival to hospital discharge with mRS \leq 3, 3- and 6-month survival overall and with mRS \leq 3, functional status at discharge, 3 and 6 months (mRS and Cerebral Performance Category [CPC] score), cost per patient and cost per life saved (individual patient billings). Safety endpoints include incidence of serious adverse events (overall due to cardiac arrest and prolonged resuscitation and related to advanced perfusion strategies).

Significance. If our study results indicate potential safety and efficacy, it will provide the basis for a future multicenter clinical trial to assess definitive survival benefit and generalizability of this approach.

